4.3. Removal of Subjects from Therapy/Premature Discontinuation

Subjects will be encouraged to complete the study and all assessments; however, subjects may voluntarily withdraw at any time.

A Subject will be discontinued from the study for the following medical or administrative reasons:

- Subject request
- Pregnancy
- Significant non-compliance with study procedures

The Investigator may discontinue individual subjects from the study at any time.

5. TREATMENTS

5.1. Treatments Administered

Study drugs will be administered by qualified research staff in accordance with the procedures described in this protocol and in the Instructions for Use.

5.2. Identity of Investigational Product

Study Drug: SCP-111 (furosemide injection), 80 mg/1 mL is a proprietary furosemide formulation that is isotonic and buffered to a neutral pH for subcutaneous administration.

SCP-111 (furosemide injection), 1 mL buffered furosemide solution (80 mg/1 mL), is manufactured by Ajinomoto Althea, Inc., [name], under good manufacturing practice conditions. Each 1 mL of SCP-111 contains 80 mg of furosemide and the following inactive ingredients: 9.7 mg Tromethamine, and 35 mg Benzyl Alcohol and also contains Sodium Hydroxide and Hydrochloric Acid for pH adjustment (pH range: 7.4 to 8.0).

Study Device: SCP-111 Autoinjector is an investigational single-entity drug-device combination product consisting of a prefilled syringe containing 1 mL of SCP-111 (furosemide injection), preloaded into a fixed single dose, disposable, two step mechanical autoinjector designed to administer the full dose to the subcutaneous tissue.

5.2.1. Labeling

80 mg SCP-111 Autoinjector will bear labels that meet applicable laws for an investigational drug-device combination, which may include, but is not limited to, the following information:

- Federal law statement
- Batch number
- Storage information

The Instructions for Use for the SCP-111 Autoinjector as it exists at the time of the study will be available for the Investigator and study staff.

5.2.2 Storage and Handling

Store SCP-111 Autoinjector at controlled room temperature between 20°C and 25°C (68°F and 77°F). Excursions permitted between 15°C and 30°C (59°F and 86°F). Do not refrigerate or freeze. Do not remove the autoinjector from the carton until ready for use. Protect from Light.

5.3. Method of Assigning Subjects to Treatment Groups

Subjects will be randomly assigned in a 1:1 ratio to 1 of 2 treatment sequences to receive both IV furosemide and SC SCP-111 in the abdomen in Crossover Periods (ie, IV followed by SC or vice versa).

5.4. Selection of Doses in the Study

The dose of 80 mg was selected based in part on the recommended dosage of furosemide injection, 10 mg/mL, USP for the treatment of edema associated with

congestive heart failure, renal disease and liver cirrhosis. The usual initial dose of furosemide IV is 20 to 40 mg given as a single dose slowly over 1 to 2 minutes. If needed, another dose may be administered in the same manner 2 hours later.

5.5. Selection and Timing of Dose for Each Subject

- **Furosemide injection 10 mg/mL, USP:** Hospira furosemide injection, solution 10 mg/mL, (NDA 018667), administered intravenously 40 mg over 1 to 2 minutes by IV injection followed by a second dose of 40 mg administered over 1 to 2 minutes, 2 hours later (reference treatment).
- **SCP-111 (furosemide injection 80 mg/1 mL):** SCP-111, furosemide injection 80 mg/1 mL for subcutaneous administration, (total dose = 80 mg dose) administered as a subcutaneous injection (test treatment) via an autoinjector.

5.6. Procedures for Blinding

This is an open label study.

5.7. Prior and Concomitant Therapy

Prior and concomitant therapy will include all prescription and non-prescription medications including over-the-counter (OTC) weight loss medications and nutritional supplements seven (7) days prior to enrollment. All information on prior and concomitant therapy will be recorded in the Subject's source and on the Subject's electronic case report form (eCRF). Requisite details will include the name of the therapy or drug and duration of the treatment (start and stop dates) and reason for use.

5.8. Prohibited Medications

Concomitant or any use within past 30 days of drugs known to interact with furosemide, including aminoglycoside antibiotics, ethacrynic acid, salicylates, cisplatin and nephrotoxic drugs, paralytic agents, lithium, angiotensin converting enzyme inhibitors or angiotensin II receptor blockers, antihypertensive drugs, adrenergic blocking drugs or peripheral adrenergic blocking drugs, norepinephrine, chloral hydrate, methotrexate and other drugs undergoing renal tubular secretion, cephalosporin, cyclosporine, thyroid hormones, phenytoin, or indomethacin is not permitted.

If a Subject is receiving oral furosemide, bumetanide or torsemide, the Subject must discontinue the therapy for 24 hours prior to being dosed with the reference or test treatment.

5.9. Study Stopping Criteria

The study may be stopped if the Investigator, Independent Medical Monitor, Sponsor or IRB determines that Subject safety may be compromised by continuing in the study.

5.10. Treatment Compliance

Study drug will be administered in accordance with the procedures outlined in this protocol. All study medication will be administered by designated study personnel and all information regarding study drug administration will be documented.

5.11. Study Drug Accountability

Only authorized site personnel may supply or administer study drug and only Subjects enrolled in the study may receive study drug, in accordance with applicable regulatory requirements.

Study staff authorized to handle and store the study drug will keep an accurate accounting of the receipt and disposition of the study drugs received from the Sponsor. Drug accountability will be assessed by the study monitor during periodic monitoring visits. At the end of the study, following final product reconciliation by the monitor, the study site will be instructed by the Sponsor as to disposition of used and unused study drug and supplies.

6. STUDY PROCEDURES

6.1. Study Measurements and Assessments

6.1.1. Assessment of Efficacy

Efficacy of the SCP-111 autoinjector combination product is being assessed based on the determination of bioavailability of a subcutaneous injection of SCP-111 80 mg compared to furosemide 80 mg administered intravenously as two 40 mg injections over 1 to 2 minutes, 2 hours apart. Urine output and urinary sodium and potassium excretion from time 0-6, 0-8 and 0-12 hours will also be assessed.

6.1.2. Assessment of Safety

Subjects will be monitored for adverse events which will be recorded and reported on the eCRF according to guidelines specified by the United States FDA and detailed in Section 7. Adverse Events. Blood pressure, heart rate, clinical chemistry labs will be collected throughout both treatment phases as outlined in Section 6.2. Study Phases and Procedures. Injection site pain will be assessed as described in Section 6.2.2.7.

6.2. Study Phases and Procedures

The Time and Event Schedule outlining study phases and procedures is provided in [Appendix 1](#).

The Screening Phase will be conducted on an outpatient basis between 14 and 3 days prior to Baseline. Subjects will be instructed to maintain a < 2 gram sodium diet and abstain from caffeine-containing products within 2 days prior to Baseline. Baseline/CRU Admission will occur on Day 0. Study drug will be administered on

Day 0 and Day 3 (± 1 day) with a 3 ± 1 day outpatient fluid washout phase between doses. Subjects will be instructed to continue a < 2 -gram sodium diet and abstain from caffeine-containing products through Day 0, the washout phase and Day 3 study drug administration. Follow-up visit will occur 24-48 hours after discharge from the CRU for Crossover Period 2.

Collection of the PK samples should occur as close to the scheduled time point as possible. The actual times of PK sample collections will be recorded. Assessments that are to be performed at the same time as a PK sample is to be drawn may be performed just prior to the collection of PK sample.

6.2.1. Study Phases

6.2.1.1. Screening (Day -14 through -3)

Subjects can be pre-screened ahead of enrollment by telephone and invited to the research center. Upon arrival to the research center, the study procedures will be explained. All Subjects who sign the informed consent form and satisfy the inclusion/exclusion criteria will be enrolled into the study.

The initial Screening visit will be conducted between 14 and 3 days prior to Baseline/CRU Admission on Day 0. The following procedures/assessments will be performed at Screening:

1. Informed consent (must be done prior to **any** of the following procedures, including asking subjects to discontinue prohibited medications)
2. Eligibility review
3. Medical history and demographics
 - Date of birth
 - Sex
 - Race
 - Ethnicity
 - Height (in)
 - Weight (lbs)
 - BMI (calculated from height and weight)
 - Medical History (self-reported; include onset dates)
 - Heart Failure
 - Hypertension
 - Stroke
 - Myocardial infarction
 - Unstable angina
 - Atrial fibrillation/flutter
 - Presence of implanted ventricular assist device, cardiac defibrillator, CardioMEMS™ or pacemaker

- Chronic obstructive pulmonary disease
 - Diabetes mellitus
 - Hepatic/liver disease
 - Chronic Kidney disease (If yes, stage)
 - Stage 1: Normal kidney function (GFR >90 mL/min/1.73 m² with urine findings, structural abnormalities, or genetic traits)
 - Stage 2: Mildly reduced kidney function (GFR (60-89 mL/min/1.73 m²))
 - Stage 3a: Moderately reduced kidney function (GFR (45-59 mL/min/1.73 m²))
 - Stage 3b: Moderately reduced kidney function (GFR 30-44 mL/min/1.73 m²)
 - Stage 4: Severe reduced kidney function (GFR 15-29 mL/min/1.73 m²)
 - Stage 5: Kidney failure (GFR < 15 mL/min/1.73 m² or dialysis)
 - Depression
 - Hyperlipidemia
 - Obstructive sleep apnea
 - Current Smoker (not current smoker if stopped smoking for at least 12 months)
4. Complete/full physical examination as described in Section 6.2.2.1
 5. Temperature
 6. Blood pressure
 7. Heart rate
 8. Screening labs will be performed to measure sodium, potassium, calcium, chloride, magnesium, carbon dioxide, blood urea nitrogen, serum creatinine, glucose, hemoglobin, hematocrit and blood alcohol.
 9. Urine drug screen
 10. Serum pregnancy test (for females of child-bearing potential)
 11. 12-Lead ECG as described in 6.2.2.2
 12. Prior medication assessment
 - If a Subject is receiving oral furosemide, bumetanide or torsemide, the Subject must discontinue the therapy for 24 hours prior to Baseline/CRU admission.
 13. Schedule next study visit (Baseline/CRU admission)

6.2.1.2. Baseline Assessment (Day 0)

Subjects will be admitted to the CRU on Day 0 (the day of study drug administration) for Baseline assessment and procedures. Low sodium diet (< 2 gram per day) and fluid intake ad libitum consisting of water, juice and caffeine free beverages are permitted while domiciled in the CRU. Subjects will be monitored during the study to ensure a minimum of 100 mL of fluid consumed for every 300 mL of urine output.

The following assessments will be completed at Baseline upon CRU admission:

1. Eligibility re-review
2. Limited physical examination as described in Section 6.2.2.1
3. Prior medication assessment
 - Time and date of last dose of oral loop diuretic (if receiving)
4. Weight measurement
5. Temperature
6. Blood pressure
7. Heart rate
8. Clinical laboratory tests as described in Section 6.2.2.3
9. Alcohol breath test
10. Urine drug screen
11. Urine pregnancy test as applicable
12. Randomization to treatment sequence
13. Photograph of Injection Site as described in Section 6.2.2.8

6.2.1.3. Treatment Crossover Period 1 (Day 0)

All subjects will remain domiciled in the CRU through the 12-hour post-dose PK sample. Subjects will be discharged from the CRU if safety parameters are acceptable to the Investigator.

6.2.1.3.1. Pre-dose

The following assessments will be completed prior to dosing:

1. Void bladder immediately before dosing and discard as described in Section 6.2.2.5
2. Plasma sample for pharmacokinetics as described in Section 6.2.2.6
3. Assessment of injection site pain as described in Section 6.2.2.7

6.2.1.3.2. Dosing

For the purpose of assessments and pharmacokinetic sampling times, Day 0, Hour 0 will be defined as the point at which study drug dose is initiated/administered. IV furosemide or SC SCP-111 should be administered according to the randomization schedule. IV furosemide is administered via IV injection as a 40 mg dose over 1 to 2 minutes followed by a second dose of 40 mg over 1 to 2 minutes, 2 hours after the

start of the initial IV dose. SC SCP-111 is administered as a single 80 mg dose via the autoinjector.

6.2.1.3.3. Post-Dose (Hour 0-12)

The following assessments will be completed beginning after the initial dose:

1. Blood pressure (15, 30 minutes and Hour 1, 2, 2.5, 3, 4, 6, 8 and 12)
2. Heart rate (15, 30 minutes and Hour 1, 2, 2.5, 3, 4, 6, 8 and 12)
3. Plasma sample for pharmacokinetics as described in Section 6.2.2.6
4. Clinical laboratory tests as described in Section 6.2.2.3 (Hour 12)
5. Urine collection from spontaneous voids for time periods (0-1), (1-2), (2-3), (3-4), (4-5), (5-6), (6-7), (7-8), (8-10) and (10-12) hours post-dose for urine volume and urinary sodium and potassium as described in Section 6.2.2.5
6. Food, snack and fluid intake and recording as per Time and Event Schedule
7. Assessment of injection site pain as described in Section 6.2.2.7
8. Adverse events
9. Concomitant medications
10. Limited physical examination as described in Section 6.2.2.1 (Hour 12)
11. Weight measurement (Hour 12)
12. Photograph of Injection Site (4 hours post IV administration or 6 hours post SC administration) as described in Section 6.2.2.8
13. Schedule next study visit
14. Discharge from the CRU if safety parameters are acceptable to the investigator (Hour 12)

6.2.1.4. Washout (Days 3 ± 1)

1. Adverse events
2. Concomitant medications
3. Low sodium diet and abstain from caffeine-containing products

6.2.1.5. Pre-Period 2 Assessment (Day 3 ± 1)

Subjects will present to the CRU on Day 3 ±1 for Pre-Period 2 assessment and procedures. Low sodium diet and fluid intake ad libitum consisting of water, juice and caffeine free beverages are permitted while domiciled in the CRU. Subjects will be monitored during the study to ensure a minimum of 100 mL of fluid consumed for every 300 mL of urine output.

The following assessments will be completed at the Pre-period 2 assessment upon CRU admission:

1. Limited physical examination as described in Section 6.2.2.1
2. Concomitant medication assessment

- a. Time and date of last dose of oral loop diuretic (if receiving)
3. Weight measurement
4. Temperature
5. Blood pressure
6. Heart rate
7. Clinical laboratory tests as described in Section 6.2.2.3
8. Alcohol breath test
9. Urine drug screen
10. Urine pregnancy test as applicable
11. Adverse events

6.2.1.6. Treatment Crossover Period 2 (Day 3 ± 1)

All subjects will remain domiciled in the CRU through the 12-hour post-dose PK sample. Subjects will be discharged from the CRU if safety parameters are acceptable to the Investigator.

6.2.1.6.1. Pre-dose

The following assessments will be completed prior to dosing:

1. Void bladder immediately before dosing and discard as described in Section 6.2.2.5
2. Plasma sample for pharmacokinetics as described in Section 6.2.2.6
3. Assessment of injection site pain as described in Section 6.2.2.7
4. Photograph of Injection Site as described in Section 6.2.2.8
5. Adverse events

6.2.1.6.2. Dosing

For the purpose of assessments and pharmacokinetic sampling times, Day 3, Hour 0 will be defined as the point at which study drug dose is initiated/administered. IV furosemide or SC SCP-111 should be administered according to the randomization schedule. IV furosemide is administered via IV injection as a 40 mg dose over 1 to 2 minutes followed by a second dose of 40 mg over 1 to 2 minutes, 2 hours after the start of the initial IV dose. SC SCP-111 is administered as a single 80 mg dose via the autoinjector.

6.2.1.6.3. Post-Dose (Hour 0-12)

The following assessments will be completed beginning after the initial dose:

1. Blood pressure (15, 30 minutes and Hour 1, 2, 2.5, 3, 4, 6, 8 and 12)
2. Heart rate (15, 30 minutes and Hour 1, 2, 2.5, 3, 4, 6, 8 and 12)
3. Plasma sample for pharmacokinetics as described in Section 6.2.2.6
4. Clinical laboratory tests as described in Section 6.2.2.3 (Hour 12)

5. Urine collection from spontaneous voids for time periods (0-1), (1-2), (2-3), (3-4), (4-5), (5-6), (6-7), (7-8), (8-10) and (10-12) hours post-dose for urine volume and urinary sodium and potassium as described in Section 6.2.2.5
6. Food, snack and fluid intake and recording as per Time and Event Schedule
7. Assessment of injection site pain as described in Section 6.2.2.7
8. Adverse events
9. Concomitant medications
10. Limited physical examination as described in Section 6.2.2.1 (Hour 12)
11. Weight measurement (Hour 12)
12. Photograph of Injection Site (4 hours post IV administration or 6 hours post SC administration) as described in Section 6.2.2.8
13. Schedule next study visit
14. Discharge from the CRU if safety parameters are acceptable to the investigator (Hour 12)

6.2.1.7. Follow-Up (Day 5 ± 1)

Follow-up visit should occur 24-48 hours after discharge from CRU for Crossover Period 2.

1. Complete/full physical examination as described in Section 6.2.2.1
2. Weight measurement
3. Blood pressure
4. Heart rate
5. Adverse events
6. Concomitant medications

6.2.2. Study Procedures

6.2.2.1. Physical Examination

At Screening and Follow-up, a complete/full physical examination should be performed. At Baseline assessment Day 0 and on Day 3 a limited physical examination may be performed consisting of assessments of the skin, lungs/chest, heart, extremities, abdomen and any other abnormalities detected during the study period. Post-dose physical examination on Day 0 and Day 3 should be performed 12 hours after the study drug is administered.

6.2.2.2. 12-lead ECG

At Screening a 12-lead ECG will be performed after the Subject has rested quietly for at least 5 minutes in a supine position.

6.2.2.3. Clinical Laboratory Tests

All clinical samples will be analyzed by a licensed clinical laboratory. The clinical laboratory tests are as follows:

6.2.2.3.1 Screening:

Blood Clinical Chemistry: sodium, potassium, calcium, chloride, magnesium, carbon dioxide, blood urea nitrogen, serum creatinine, glucose, hemoglobin, hematocrit, and blood alcohol.

Serum pregnancy test in females of childbearing potential: beta hCG

Urine Drug Screen: Subjects with positive urine drug screen test results will be excluded from the study.

6.2.2.3.2 Pre-Dose and Post-Dose

Blood Clinical Chemistry: sodium, potassium, calcium, chloride, magnesium, carbon dioxide, blood urea nitrogen, serum creatinine, glucose, hemoglobin, hematocrit.

Post-dose clinical labs on Day 0 and Day 3 should be performed 12 hours after the study drug is administered.

The Investigator is responsible for determining if out of range laboratory values are clinically significant or not. All clinically significant values will be followed until stabilization, resolution, or loss to follow-up.

6.2.2.4. Temperature, Blood Pressure and Heart Rate

Temperature (oral or equivalent) will be taken. Blood pressure (mmHg) and heart rate (bpm) will be measured in the supine position after the Subject has rested comfortably for at least 5 minutes.

Height and weight will be collected and BMI will be calculated. Height collected at Screening only.

6.2.2.5. Urine Collection

Subjects will be instructed to void in order to empty their bladder immediately before dosing (pre-dose urine). The pre-dose urine will be **discarded**. Dosing should not commence if the Subject has not emptied their bladder in the previous 60 minutes. Urine from spontaneous voids during the post-dose phases will be collected and pooled, measured, recorded for time periods (0-1), (1-2), (2-3), (3-4), (4-5), (5-6), (6-7), (7-8), (8-10) and (10-12) hours after initiation of dosing. Urine for each collection period must be collected in a single vessel and refrigerated until the end of the collection period. An aliquot of urine from each time period will be collected and sent for urinary sodium and urinary potassium. Urinary sodium and urinary potassium concentration for each collection interval over the 12-hour urine collection period will be analyzed by standard lab biochemistry test. The 6-hour, 8-hour and 12-hour urinary sodium and potassium excretion will be determined and compared for each treatment group. Total urine output volume will be documented for each collection period.

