	
Secondary Endpoints:
 
Pharmacokinetics/pharmacodynamics
 
The following pharmacokinetics (PK) parameters will be evaluated for subcutaneous and intravenous furosemide administration:
 
• Maximum observed plasma concentration (C_{max})• Time to C_{max} (T_{max})• Terminal phase elimination rate constant (λ_z), estimated by linear regression of logarithmically transformed concentration versus time data• Terminal elimination half-life ($t_{1/2}$) estimated using the equation $[\ln(2)/\lambda_z]$• Apparent systemic clearance (CL/F)• Systemic clearance (CL)• Apparent systemic volume of distribution (Vz/F)• Systemic volume of distribution (V) 
The following pharmacodynamics (PD) parameters will be evaluated for subcutaneous and intravenous furosemide administration:
 
• Urine output (0-6, 0-8, and 0-12 hours)• Urinary sodium excretion (0-6, 0-8, and 0-12 hours)• Urinary potassium excretion (0-6, 0-8, and 0-12 hours) 
Safety and tolerability
 
Safety
 
Adverse Events (AEs) and Serious Adverse Events (SAEs) will be grouped by body system and summarized. The incidence (number and percentage of subjects) of adverse events and

--	--

	
serious adverse events will be presented overall and by MedDRA System Organ Class and Preferred Term.
 
Injection Site Pain
 
Injection site pain will be assessed using an 11-point scale where 0 is equivalent to no pain and 10 is equivalent to the worst possible pain. For IV administration, the 11-point pain scale will be performed pre-dose after IV needle placement, immediately after 1st dose and 15 and 30 minutes after 1st dose, immediately after 2nd dose and 15 and 30 minutes and 4 and 10 hours after the 2nd dose. For SC administration, the 11-point pain scale will be performed pre-dose, immediately after dose and 15 and 30 minutes and 6 and 12 hours after dose. Pain requiring treatment, withdrawal from the study or discontinuation of study drug will also be recorded as an adverse event (AE).

STUDY DURATION
	
4 months

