3. INVESTIGATIONAL PLAN

3.1. Overall Study Design and Plan

This is an open-label, single-center, single-dose, randomized, two-way (two-period) crossover study in healthy volunteers. Each Subject will complete Screening, Baseline, Treatment, and Follow-up Phases.

The Screening Phase will be conducted on an outpatient basis between 14 and 3 days prior to the Baseline visit. Subjects will be instructed to maintain a < 2-gram sodium diet and abstain from caffeine-containing products within 2 days prior to admission to the CRU. On arrival to the CRU (Day 0), baseline and final qualification assessments will be performed.

The Treatment Phase will be comprised of two crossover periods separated by a 3 ± 1 day washout period. During each CRU admission and through the washout period, Subjects will continue a < 2-gram sodium diet and abstain from caffeine-containing products. Subjects will be randomly assigned in a 1:1 ratio to 1 of 2 treatment sequences to receive IV furosemide and SC SCP-111 in the abdomen in Crossover Periods (ie, IV followed by SC or vice versa). Blood samples will be collected to measure plasma furosemide concentrations at pre-dose and for 12 hours post-dose. Prior to dosing in each Treatment Phase, subjects will void their bladder completely and urine will be collected starting after the injection through 12 hours post injection to determine total urine output and urinary sodium and potassium excretion. Assessment of injection site pain will be conducted for IV and SC administration using an 11-point pain scale. Photographs of the injection site will be performed prior to the IV and SC injection (baseline) and 4 hours post IV administration and 6 hours post SC administration. In addition, a photograph will be taken of the IV and SC injection site for any AE (i.e., erythema, edema, pruritus, bruising) that occurs at the site at the time of the event. Subjects will remain domiciled in the CRU for each Crossover Period during the Treatment Phase through 12 hours after administration of study drug. After final assessments are performed, Subjects may be discharged from the CRU if safety parameters are acceptable to the Investigator.

The Follow-up Phase will occur 24-48 hours (Day 5 ± 1) after discharge from the CRU following Crossover Period 2, completing Subjects' study participation.

[figure not shown]

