- ⁴ Clinical labs include sodium, potassium, calcium, chloride, magnesium, carbon dioxide, blood urea nitrogen (BUN), serum creatinine, glucose, hemoglobin, and hematocrit. Post-dose clinical labs on Day 0 and Day 3 should be performed 12 hours after the study drug is administered.
- ⁵ Pregnancy test for females of child-bearing potential.
- ⁶ Intravenous furosemide is administered as 40 mg over 1 to 2 minutes followed by a second dose of 40 mg over 1 to 2 minutes, 2 hours apart by IV injection. SCP-111 is administered as a single, 80-mg dose by subcutaneous injection via an autoinjector.
- ⁷ Pharmacokinetic sampling per instructions in 6.2.2.6
- ⁸ Subjects will be instructed to void immediately before dosing (pre-dose urine) and this sample will be discarded. Urine from spontaneous voids during post-dose phases will be collected and pooled, measured, recorded for time periods (0-1), (1-2), (2-3), (3-4), (4-5), (5-6), (6-7), (7-8), (8-10) and (10-12) hours after initiation of dosing. Urine from each collection period must be collected in a single vessel and refrigerated until the end of the collection period. Urinary sodium and urinary potassium concentrations for each collection interval over the 12-hour urine collection period will be analyzed by standard lab biochemistry test. Total urine output volume will be documented for each collection period.
- ⁹ Low sodium snacks and meals as well as water, juice, and caffeine free beverages will be allowed ad libitum, and the amount measured and recorded over the post-dose phases. Subjects will be monitored to ensure a minimum of 100 mL of fluid consumed for every 300 mL of urine output.
- ¹⁰ Assessment of injection site pain for IV administration performed pre-dose after IV needle placement, immediately after 1st dose and 15 and 30 minutes after 1st dose, immediately after 2nd dose and 15 and 30 minutes and 4 and 10 hours after the 2nd dose. For SC administration, injection site pain conducted pre-dose, immediately after dose and 15 and 30 minutes and 6 and 12 hours after dose.
- ¹¹ Photographs of the injection site will be performed prior to the IV and SC injection (baseline) and 4 hours post IV administration or 6 hours post SC administration. In addition, a photograph will be taken of the IV and SC injection site for any AE (i.e., erythema, edema, pruritus, bruising) that occurs at the site at the time of the event.

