6.2. Pharmacodynamic Endpoints

Urine will be collected from spontaneous voids in 1-hour increments for the first 8 hours and in 2-hour increments up to 12 hours post-dose. Total urine output, urinary sodium, and potassium excretion for each collection interval ((0-1), (1-2), (2-3), (3-4), (4-5), (5-6), (6-7), (7-8), (8-10) and (10-12) hours after initiation of dosing) will be recorded.

The following PD parameters will be evaluated for IV furosemide and SC SCP-111 subcutaneous administration:

Urine Output:

- Measured at 0-6 hours, 0-8 hours, and 0-12 hours
- The sum of urine output for intervals 0-1, 1-2, 2-3, 3-4, 4-5 and 5-6 comprise 0–6-hour urine output.
- The sum of urine output for intervals 0-1, 1-2, 2-3, 3-4, 4-5, 5-6, 6-7 and 7-8 comprise 0–8-hour urine output.
- The sum of urine output for intervals 0-1, 1-2, 2-3, 3-4, 4-5, 5-6, 6-7, 7-8, 8-10 and 10-12 comprise 0–12-hour urine output.

Urinary Sodium Excretion:

- Measured at 0-6 hours, 0-8 hours, and 0-12 hours
- Calculated as: Urinary Sodium Excretion=Total Urine Output (L) × Sodium Concentration (mEq/L)

Urinary Potassium Excretion:

- Measured at 0-6 hours, 0-8 hours, and 0-12 hours
- Calculated as: Urinary Potassium Excretion=Total Urine Output (L) × Potassium Concentration (mEq/L)

Example Calculation:

- **Interval: 0-1 hour**

Total Urine Output=0.5 L

Sodium Concentration=100 mEq/L

Urinary Sodium Excretion=0.5 L×100 mEq/L=50 mEq

- **Interval: 1-2 hours**

Total Urine Output=0.4 L

Sodium Concentration=90 mEq/L

Urinary Sodium Excretion=0.4 L×90 mEq/L=36 mEq

Continue this calculation for each subsequent interval (e.g., 0-1, 1-2, 2-3, 3-4, 4-5, 5-6, 6-7, 7-8, 8-10, and 10-12 hours) to obtain the total urinary sodium excretion for each time period.

Same calculations are conducted to calculate urinary potassium excretion for each interval.

The sum of intervals 0-1, 1-2, 2-3, 3-4, 4-5 and 5-6 comprise 0-6 hour urinary sodium/potassium excretion.

The sum of intervals 0-1, 1-2, 2-3, 3-4, 4-5, 5-6, 6-7 and 7-8 comprise 0-8 hour urinary sodium/potassium excretion.

The sum of intervals 0-1, 1-2, 2-3, 3-4, 4-5, 5-6, 6-7, 7-8, 8-10 and 10-12 comprise 0-12 hour urinary sodium/potassium excretion.

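### Urine is collected only from spontaneous voids, with no void requested at 6, 8 or 12 hours, so the secondary PD totals carry an uncontrolled boundary error

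*Protocol*

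**What the plan says.** The PD endpoints in the Protocol synopsis are secondary. They are "Urine output (0-6, 0-8, and 0-12 hours") and sodium and potassium excretion over the same windows.

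The collection rule is the same wherever it appears:

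- Protocol 6.2.2.5: "Urine from spontaneous voids during the post-dose phases will be collected and pooled, measured, recorded for time periods", followed by ten clock-time bins.
- Protocol Appendix 1, footnote 8: "Urine from spontaneous voids during post-dose phases will be collected and pooled, measured, recorded for time periods", with the same bins.
- SAP 6.2: "Urine will be collected from spontaneous voids in 1-hour increments for the first 8 hours and in 2-hour increments up to 12 hours post-dose". Protocol 3.1.1, 3.2.2, 6.2.1.3.3 and 6.2.1.6.3 agree.

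The start of collection has an instructed void. Protocol 3.1 says that "subjects will void their bladder completely and urine will be collected starting after the injection through 12 hours post injection", and Protocol 6.2.1.3.1 lists "Void bladder immediately before dosing and discard as described in Section 6.2.2.5". Protocol 6.2.2.5 adds a limit: "Dosing should not commence if the Subject has not emptied their bladder in the previous 60 minutes".

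The end of collection has no counterpart. The Hour 12 items in Protocol 6.2.1.3.3 and 6.2.1.6.3 include laboratory tests, physical examination, weight and discharge, but no final void. Actual times are required for PK samples (Protocol 6.2 and 6.2.2.6) but not for voids. Need for a catheter is an exclusion (Protocol 4.2, item 11).

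SAP 6.2 builds each total by adding its bins. SAP 9.2 compares SC with IV in a mixed model with 95% confidence intervals and p-values. SAP 4.4 drops a subject from a window if any of its bins is missing, and does not say whether a bin without a void is missing or zero.

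**The concern.** Each window is meant to capture what the kidneys excreted up to a fixed time, but the rule captures what the subject chose to void by then. A subject who voids at 5 h 10 min and again at 6 h 10 min has 50 minutes of urine left out of the 0-6 hour total and booked to 6-7 hours. Whatever is in the bladder at 12 hours is not collected at all. The size of the error depends on voiding habit, not on treatment, and it enters volume, sodium and potassium together.

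At stake are the accuracy of the absolute totals and the precision of the SC-IV differences, in a study planned for 18 completers. The error cannot be repaired afterwards: urine remaining at 12 hours is gone, and without void times the 6 and 8 hour cut-offs cannot be adjusted. Hourly bins filled only by spontaneous voids will also often be empty, which brings the undefined missing-bin rule into play.

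**Working it through.** **What can be reproduced.** The plan states no expected value, variance or sample size for the PD totals. Its sample size of 18 completers (21 enrolled) rests on AUCinf alone and is not affected.

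**Step 1: identity, from the text alone.**

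Recorded(0-T) = produced(0-T) − bladder content at T + urine held at dosing.

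At T = 6 or 8 hours the second term passes to a later bin and is still counted in 0-12 hours if voided by then. At T = 12 hours it is lost. The third term enters the 0-1 hour bin and so every cumulative total.

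**Step 2: size under assumed voiding habits.** Assume void volumes V are lognormal with median m and log-SD 0.35, and that the cut-off falls at random within the filling cycle (by volume). Then:

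- E[V] = m·exp(0.35²/2) = 1.063m
- E[V²] = m²·exp(2 × 0.35²) = 1.278m²
- E[V³] = m³·exp(4.5 × 0.35²) = 1.735m³
- Mean content = E[V²]/(2E[V]) = 0.60m
- SD of content = √(E[V³]/(3E[V]) − 0.601²m²) = √(0.544 − 0.361)·m = 0.43m

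| Assumed median void | Mean content at cut-off | SD per subject-period | SD added to one SC-IV difference (×√2) |
|---|---|---|---|
| 200 mL | 120 mL | 86 mL | 121 mL |
| 300 mL | 180 mL | 128 mL | 181 mL |
| 400 mL | 240 mL | 171 mL | 242 mL |

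These sizes follow entirely from the assumed void volume. Nothing from the documents enters them.

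**Step 3: sensitivity to the assumptions.** A simulation assumed about 2.6 L over 12 hours, two flow peaks for IV and one broader peak for SC. Voids occurred at about 200, 300 or 400 mL, or at latest every 2, 3 or 4 hours.

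| Cut-off | Mean shortfall | SC-IV produced | SC-IV recorded | Shift |
|---|---|---|---|---|
| 6 h | 3.9-10.9% | −190 mL | −205 to −211 mL | 15-21 mL |
| 8 h | 2.9-8.7% | −99 mL | −121 to −150 mL | 22-51 mL |
| 12 h | 2.4-5.5% | −28 mL | −34 to −44 mL | 6-16 mL |

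In this model the SD per subject-period was 38-133 mL, lower than in step 2 because the time limit forces earlier voids. At least one bin was empty in 68-100% of subject-periods, with a mean of 0.7 to 3.9 empty bins out of 10.

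**Step 4: the offset at the start.** If a subject were dosed a full 60 minutes after the last void, an assumed 1-2 mL/min gives 60 × 1 to 60 × 2 = 60-120 mL carried into 0-1 hour. Set against 120-240 mL, that is between a quarter (60/240) and all (120/120) of the mean shortfall.

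**Step 5: effect on precision.** With 18 subjects, the SD of 121-242 mL from step 2 corresponds to 121/√18 to 242/√18 = 29-57 mL, combined in quadrature with all other variation. If the SD of the difference were otherwise 500 mL (assumed), it would become √(500² + 121²) = 514 mL to √(500² + 242²) = 555 mL, a rise of 3-11%.

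**The case against.** The strongest reply is that the harm is modest and falls on secondary endpoints. The objective is to describe the pharmacodynamics, Protocol 8.5 is descriptive, and no PD acceptance limit exists. Both arms follow the same procedure, and volume voided per clock interval is a coherent measure. This largely stands and limits the weight of the point. It does not remove it, because SAP 9.2 attaches confidence intervals and p-values to these totals.

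A reader might infer that the totals fail to measure their windows. The documents do not support that: they measure the windows with error, and only the 12-hour remainder is lost.

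A reader might also infer that output is always understated. The offset in step 4 acts in the other direction, so the net sign for an individual is not fixed.

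A third tempting reading is that the SC-IV comparison is materially biased. The arm means of the error are similar in the illustrative models. Exact cancellation is not assured when one SC dose is set against two IV doses 2 hours apart, but the modelled shifts are small and depend on assumed flow curves.

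Finally, the 60-minute sentence might be read as licensing an hour of pre-dose urine. Protocol 6.2.2.5 itself says that "Subjects will be instructed to void in order to empty their bladder immediately before dosing (pre-dose urine"), and the limit reads naturally as a backstop. The two statements need reconciling; they do not show a defective start of collection.

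**Conclusion.** The point holds as a cheap improvement. Nothing in either document requests a void at the end of any window or requires void times, so the 0-6, 0-8 and 0-12 hour totals carry an uncontrolled boundary error. That conclusion rests on the text alone.

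The size is illustrative only. For assumed typical voids of 200-400 mL, the mean is about 120-240 mL per cut-off and the SD about 85-170 mL per subject-period, before any offset from urine held at dosing. Different assumptions about voiding give smaller figures. The main consequences are added noise in the SC-IV differences and somewhat inaccurate absolute totals. The primary AUC analysis, its 80-125% criterion and the sample size are not touched.

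**What to change.** - In Protocol 6.2.2.5 and Appendix 1 footnote 8, ask subjects to try to empty the bladder just before the end of the 6, 8 and 12 hour windows, ideally every bin. Credit that void to the bin that is ending, and record actual void times.
- Time the attempt so that the supine rest of at least 5 minutes before blood pressure (Protocol 6.2.2.4) is kept.
- In SAP 4.4, state that a bin with no void counts as 0 mL, and hence 0 mEq of sodium and potassium, and is not missing. Otherwise the exclusion rule could remove the subject from the window. Keep missing for urine that was passed but lost or not measured.
- Reconcile the 60-minute sentence in Protocol 6.2.2.5 with the instruction on the timing of the pre-dose void.

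The cost is a few sentences. Subjects are already in the unit, with blood pressure and PK sampling at 6, 8 and 12 hours in both arms (for IV, 4, 6 and 10 hours on the second-dose clock). Pain is scored at 6 and 12 hours but not at 8. The downside is that voids at the cut-offs become prompted, and some attempts will yield nothing.
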